### 11.3 Vital Signs

Descriptive statistics will be presented by scheduled visit for the actual values and the changes and percentage changes from baseline for each vital sign. The maximum post baseline systolic blood pressure categories ( $< 140$  mmHg,  $140 - < 160$  mmHg,  $160 - < 180$  mmHg and  $\geq 180$  mmHg) will be summarized using counts and percentages. This analysis will also be performed by baseline use of anti-hypertensives (yes/no). The anti-hypertensives are the medications with any of the following ATC codes at baseline: C02 (anti-hypertensives), C03 (diuretics), C04 (peripheral vasodilators), C07 (beta blocking agents), C08 (calcium channel blockers), and C09 (agents acting on the rennin-angiotensin system). These analyses will be repeated for maximum post baseline diastolic blood pressure categories ( $< 90$  mmHg,  $90 - < 100$  mmHg,  $100 - < 110$  mmHg and  $\geq 110$  mmHg).

The number and percentage of following types of patients will be presented:

- Patients with systolic BP  $\geq 140$  mmHg or diastolic BP  $\geq 90$  mmHg at consecutive visits (2 or more visits, 3 or more visits) of present study
- Patients with systolic BP  $\geq 140$  mmHg or diastolic BP  $\geq 90$  mmHg anytime during the post-baseline of present study
- Patients with systolic BP  $\geq 160$  mmHg or diastolic BP  $\geq 100$  mmHg at consecutive visits (2 or more visits, 3 or more visits) of present study
- Patients with systolic BP  $\geq 160$  mmHg or diastolic BP  $\geq 100$  mmHg anytime during the post-baseline of present study
- Patients with systolic BP  $\geq 180$  mmHg or diastolic BP  $\geq 110$  mmHg at consecutive visits (2 or more visits, 3 or more visits) of present study
- Patients with systolic BP  $\geq 180$  mmHg or diastolic BP  $\geq 110$  mmHg anytime during the post-baseline of present study

In addition, shifts based on new guidance in blood pressure (**Appendix 14.3**) from normal, elevated, Stage 1, Stage 2 and hypertensive crisis at baseline to normal, elevated, Stage 1, Stage 2 and hypertensive crisis for the maximum observed value, and the last value post baseline will

be tabulated. The maximum observed blood pressure and the last blood pressure post baseline will be based on both scheduled and unscheduled visits.

Box plots indicating mean and median as well as the 25th and 75th percentiles, reference plots, and spaghetti plots will be presented by scheduled visit for both raw values and changes from baseline.

#### **11.4 IBLS and WHO Bleeding Scale Scores**

The IBLS will be analyzed as follows:

- The mean of the IBLS scores across 9 anatomical sites and across visits during the 24-month treatment period in present study will be summarized using descriptive statistics.
- The highest IBLS score across the 9 anatomical sites and the total IBLS score will be summarized by visit.

The WHO bleeding scale will be analyzed as follows:

- The mean of the WHO bleeding scale across visits during the 24-month treatment period in present study will be summarized using descriptive statistics.

In addition, both IBLS bleeding scale and WHO bleeding scale analyses mentioned above will be performed by prior study treatment group and overall.

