4.4 Safety Endpoints

Safety endpoints include the frequency and severity of bleeding according to the IBL5; change from baseline (baseline value is the value at the initiation of active therapy) in blood pressure, liver function, and ANC; the incidence and severity of gastrointestinal (GI) effects (nausea, vomiting, diarrhea, abdominal pain); infection; and overall AEs.

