7.6.4 Bleeding Assessment

Bleeding symptoms will be assessed using the IBLS at each study visit. ⁽⁴⁾ The IBLS will include assessment of bleeding at 9 anatomical sites over the past week graded from 0 (none) to 2 (marked bleeding). Assessment of bleeding at 2 sites, skin and oral, should be assessed by physical examination (see Appendix 7).

The World Health Organization bleeding scale (Appendix 8) was collected during the first 2 years of treatment, but has been discontinued in Version 4 of the protocol.

The assessor must be a physician, doctor of osteopathic medicine, physician's assistant, or nurse practitioner. The assessor must also be the same person who is performing the physical exam for the study visit. The IBLS is to be performed by the same assessor for each subject at each study visit, whenever possible.

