Appendix 7: The Immune Thrombocytopenic Purpura Bleeding Score Assessment

Site	Bleeding Score		
	0	1	2
Skin (Physical Examination (PE))	None	1–5 bruises and/or scattered petechiae	>5 bruises with size >2 cm and/or diffuse petechiae
Oral (PE)	None	1 blood blister or >5 petechiae or gum bleeding that clears easily with rinsing	Multiple blood blisters and/or gum bleeding
Skin (Hx)	None	1–5 bruises and/or scattered petechiae	>5 bruises with size >2 cm and/or diffuse petechiae
Oral (Hx)	None	1 blood blister or >5 petechiae and/or gum bleeding <5 min	Multiple blood blisters and/or gum bleeding >5 min
Epistaxis	None	Blood when blowing nose and/or epistaxis <5 min (per episode)	Bleeding >5 min (per episode)
Gastrointestinal (GI)	None	Occult blood	Gross blood
Urinary (U)	None	Microscopic (+ve dipstick)	Macroscopic
Gynecological (GYN)	None (normal period)	Spotting not at time of normal period	Bleeding >spotting not at time of period or very heavy period
Pulmonary	None	N/A	Yes
Intracranial hemorrhage	None	N/A	N/A
Subconjunctival hemorrhage	None	Yes	N/A

Source: [Page 2007](#) ⁽⁴⁾

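### SAP 11.4 plans no count of patients by worst post-baseline IBLS score, and Appendix 7 as printed leaves the intracranial row and the 9-site scoring unclear

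*SAP*

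**What the plan says.** Protocol 4.4 opens its list of safety outcomes with: "Safety endpoints include the frequency and severity of bleeding according to the" IBLS. Long-term safety is the primary objective. SAP 4.5 carries over severity but not frequency, and SAP 3.5, which records departures from the protocol's analyses, does not mention that change.

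The scale is described in Protocol 7.6.4 as "assessment of bleeding at 9 anatomical sites over the past week graded from 0 (none) to 2 (marked bleeding"). SAP 11.4 then plans three things, each by prior treatment group and overall:

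- for IBLS, a mean over sites and visits: "The mean of the IBLS scores across 9 anatomical sites and across visits during the 24-month treatment period in present study";
- also for IBLS: "The highest IBLS score across the 9 anatomical sites and the total IBLS score will be summarized by visit";
- for the WHO scale, only a mean across visits.

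SAP 11.4 does not say which statistics the by-visit IBLS summary will use.

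In Protocol Appendix 7 the row "Intracranial hemorrhage" reads None under 0 and N/A under both 1 and 2. The pulmonary row has Yes under 2, and the subconjunctival row has Yes under 1. The table has 11 rows because skin and oral bleeding are each rated twice, by examination and by history.

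**The concern.** The natural safety question is how many patients had any bleeding, and how many had marked bleeding, while on fostamatinib. No table described in SAP 11.4 answers it. Averaging over sites and visits dilutes an isolated marked bleed. A by-visit summary shows the position at each visit but does not link visits within a patient.

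The same SAP uses the patient-level approach elsewhere. Section 11.2 sets baseline laboratory grade against the worst post-baseline grade. Section 11.3 tabulates maximum post-baseline blood pressure and patients above a threshold at any time. Section 11.1 gives each patient's maximum diarrhea grade. Bleeding, the main clinical risk of the disease, has no equivalent.

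Two scoring gaps add to this. The printed intracranial row gives no way to record a positive score for that site. With no rule for combining the examination and history rows, two programmers could compute different means and totals from the same data.

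**Working it through.** The documents state no bleeding rate, target or precision, so there is no planned figure to reproduce. The check is what the planned summaries would return.

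**Inputs**
- Visits: monthly for 18 months, then every other month (SAP 3.1). To Month 24 that is 18 + 3 (Months 20, 22, 24) = 21 visits after Day 1. To Month 60 it is 18 + 21 = 39.
- Sites and range: 9 sites, each scored 0 to 2 (Protocol 7.6.4).
- Patients: up to 150 (SAP 3.1).
- Assumptions: every visit attended and all 150 patients present. The bleeding patterns below are illustrations, not figures from the documents.

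**1. What the mean does.** Patient mean = sum of scores / (sites × visits).
- One score of 2, at one site, at one visit: 2/(9 × 21) = 2/189 = 0.011.
- A score of 1 at one site at every visit: 21/189 = 1/9 = 0.111.
- Ratio: 0.111/0.0106 = 10.5 in favor of the persistent mild score.
- Over 39 visits the single marked bleed gives 2/351 = 0.0057, and the ratio is 19.5.

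The mean measures cumulative burden. It does not identify patients with a marked bleed.

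**2. What the by-visit highest score does.** Suppose it is tabulated as counts and k patients score 2 at each of 21 visits. The number who ever scored 2 is at least k (the same patients each time) and at most 21k (different patients each time).

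| Patients at 2 per visit | Fewest ever at 2 | Most ever at 2 |
|---|---|---|
| 1 | 1 (0.7%) | 21 (14%) |
| 3 | 3 (2%) | 63 (42%) |

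If the score is treated as continuous under SAP 5.1, the table gives a mean, quartiles and a maximum. A maximum of 2 shows only that at least one patient scored 2 at that visit.

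**3. The divisor.** Appendix 7 names nine distinct sites: skin, oral, epistaxis, gastrointestinal, urinary, gynecological, pulmonary, intracranial and subconjunctival. Two of them have two rows, hence 11. If all rows enter the mean, the single marked bleed in step 1 gives 2/(11 × 21) = 2/231 = 0.0087 instead of 0.011. A marked skin bleed scored 2 on both the examination and history rows adds 4 to the total if rows are summed, but 2 if they are combined by taking the higher.

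**4. The intracranial row.** The only numbered category with an entry other than N/A is 0, against None. Read literally, that site cannot raise the mean, the total or the highest score.

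**The case against.** The strongest reply is that the bleeding data are not lost. SAP 5.1 puts all data in patient listings. SAP 11.1 tabulates AEs and SAEs by preferred term at patient level, and AEs by severity. Protocol 9.1 counts newly emerging signs of the target disease as AEs, and Protocol 7.6.1 asks for new or worsened examination findings to be recorded as AEs. The by-visit highest score does use each patient's worst site at each visit. This stands: a reader might infer that the plan cannot show how many patients had a marked bleed, and the documents do not support that. What remains is that bleeding is not among the AEs of interest in SAP 4.5, so no grouped count is planned there, and a listing is not a pre-specified summary of an endpoint defined by IBLS.

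A reader might also infer that an intracranial hemorrhage would be recorded as no bleeding. No text says that N/A is scored 0. The table was extracted from a PDF, and the scale comes from a cited publication that is not available here. An event that was fatal, life-threatening or required hospitalization would be an SAE in any case. The supportable request is to check the row.

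Third, a worst IBLS score would not give the number who ever bled. The scale looks back one week, so 21 visits cover about 21 × 7 = 147 of 730 days (20%). This also stands, and the new table should be labelled accordingly.

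Finally, SAP Appendix 14.1 has seven redacted entries, so the point is confined to SAP 11.4 and the readable text.

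**Conclusion.** The point holds as a missing pre-specified summary. SAP 11.4 has no count of patients by worst post-baseline IBLS score, although the protocol endpoint includes frequency and the SAP summarizes other safety measures by patient-level worst values. The planned mean puts one marked bleed 10.5 times below persistent mild bleeding at one site over 21 visits. By-visit counts leave the number ever at score 2 undetermined over a wide range. Both results rest on full attendance and illustrative patterns; neither predicts what the trial will show.

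On Appendix 7, the conclusion is limited to what is printed: no score above 0 for intracranial hemorrhage, and no rule taking 11 rows to 9 sites. Whether the row is an error in the protocol, in the extraction or in neither cannot be settled from these documents.

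No hypothesis test or decision rule depends on these summaries. The change is worth making because the endpoint serves the primary objective and the data are already collected.

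**What to change.** - In SAP 11.4, add the number and percentage of patients whose worst post-baseline IBLS score in the present study is 1 or more, and whose worst score is 2, overall, by site and by prior treatment group. Label it as bleeding in the week before each visit. State the period it covers, since SAP 11.4 refers to 24 months and the visit schedule runs to Month 60.
- Show alongside it any intracranial hemorrhage reported as an AE or SAE.
- Check the intracranial row of Protocol Appendix 7 against the source instrument and the eCRF, and correct it if it is as printed.
- State how the examination and history rows for skin and oral bleeding combine, following the instrument, so that the mean and the total have one definition.

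The cost is one extra descriptive table from existing data, a check of one row and a sentence on scoring.

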5.3 Study Treatment

Depending on their response to treatment in Study C-935788-047 or C-935788-048 there will be two categories of subjects in this study: responders and nonresponders (see Figure 2).

- Responders will initiate open-label fostamatinib treatment with the dose and regimen that was efficacious in achieving a stable platelet response in Study C-935788-047 or C-935788-048.
- Nonresponders will initiate treatment with fostamatinib 100 mg PO *bid*. If a nonresponding subject has previously required a dose reduction (to less than 100 mg PO *bid*) due to an AE, the Sponsor's Medical Monitor should be contacted regarding the subject's eligibility and the appropriate starting dose.

Figure 2: Initial Treatment Allocation

Subjects will self-administer the study drug throughout the 60-month treatment period. Subjects on a *bid* dosing regimen will self-administer 1 tablet once in the morning and once in the evening at least 8 hours apart. Subjects on a *qd* dosing regimen will self-administer 1 tablet per day by mouth in the morning.

At the end of Month 1 (approximately Day 30), subjects receiving fostamatinib 100 mg PO *bid* should have the dose escalated to fostamatinib 150 mg PO *bid* if platelet count < 50,000/ μ L and the study drug is well tolerated (refer to [Section 7.2.1](#)).

Subjects whose platelet count is consistently < 50,000/ μ L following 3 months (12 weeks) of treatment, and at least 4 weeks at a dose of 150 mg PO *bid* (provided this higher dose was tolerated), should be discontinued from the study, unless tangible clinical benefit for the use of fostamatinib is evident and the Sponsor agrees (all instances must be reviewed with the Sponsor's Medical Monitor). Examples of tangible clinical benefit may include, but are not limited to:

- Credible increase in platelet count (eg, increase in platelet count of at least 20,000/ μ L over initial baseline to a count \geq 30,000/ μ L)
- Reduction in bleeding
- Reduction in the need for rescue therapy

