10.5 Safety Endpoints

The safety outcomes of this study include the frequency and severity of bleeding according to the IBLS, the change from baseline in blood pressure, liver function, and ANC, the incidence of GI complaints, and the incidence of AEs.

The mean of the IBLS scores across visits during the treatment period will be summarized using descriptive statistics.

Descriptive statistics will be presented by visit for the actual values and the changes from baseline for systolic and diastolic blood pressure, each liver function test [ALT, AST, alkaline phosphatase, and bilirubin (total, direct, and indirect)], and ANC. The one-sample t-test will be used to test whether the mean change from baseline equals 0 for each post-baseline time point. The numbers and percentages of patients with GI complaints at any time during the treatment period will be presented for the Safety Population.

AEs will be coded using the Medical Dictionary for Regulatory Activities (MedDRA). The number and percentage of subjects with at least one AE, at least one SAE, and at least one treatment-related AE will be presented. AEs that are possibly or probably related to study treatment, or for which the relationship to study treatment is missing, will be considered treatment related. AEs will be summarized at the subject level by MedDRA system organ class (SOC) and preferred term using frequencies and percentages. AEs will also be tabulated at the event level by severity and by relationship to study treatment.

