## 3.0 INVESTIGATIONAL PLAN

### 3.1 Overall Study Design Summary

This is a Phase 3 multi-center, open label extension study to evaluate the long-term safety and efficacy of fostamatinib in achieving and maintaining a stable platelet response in subjects with persistent/chronic Immune Thrombocytopenic Purpura (ITP). For the purpose of this study, the term ‘subject’ will refer to patients with persistent/chronic ITP participating in this study. Up to 150 subjects will be enrolled at multiple sites. The study will consist of monthly visits for 18 months followed by every-other-month visits for a maximum of 5 years of treatment or until commercial availability of drug, whichever comes first.

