**Table 1: Schedule of Study Procedures**

	Day 1 Screen/ Enrollmenta	End of Month 1 (± 3 days)	Months 2–18 (± 3 days)	Months 19– 60 (± 1 week)	Follow-up (± 7 days)i
Informed consent	X				
Inclusion/Exclusion	X				
Physical exam/KPS	X	X	monthly	every other month	X
Concomitant medications	X	X	monthly	every other month	X
Vital signs b	X	X	monthly	every other month	X
Bleeding assessment c	X	X	monthly	every other month	X
ECG	X				
Hematology d	X		monthly	every other month	X
Platelets	X	X	monthly	every other month	X
Serum chemistries (including LFTs) e	X		Months 4, 8, 12, 16	every other month	X
LFTs only f			monthly (in months full serum chemistries not done)		X
Immunoglobulin levels	X				X
Urinalysis	X		Months 4, 8, 12, 16	every 4 months	X
Urine pregnancy test g	X		every other month	every other month	
SF-36 h	X		Month 12		
AEs	X	X	monthly	every other month	X
PK			Month 2		
Study drug dispensed/Accountability	X	X	monthly	every other month	
Dose adjustment (prn)	X	X	monthly	every other month	

- a. **Screen/Enrollment (Day 1):** These procedures are equivalent to Week 24 visit of Study C-935788-047 or C-935788-048; assessments performed as part of Week 24 may be used to assess subject's eligibility to roll over and do not need to be repeated specific to Study C-935788-049.
- b. **Vital Signs:** blood pressure, pulse and temperature
- c. **Bleeding assessment:** IBLS scale only; prior to Version 4, protocol used both IBLS and WHO bleeding scales
- d. **Hematology:** CBC with differential, RBC, hemoglobin, hematocrit, MCHC, MCH, MCV, MPV, RDW, reticulocytes
- e. **Serum chemistries:** Na, K, Cl, bicarbonate (CO2), Ca, PO4, BUN, creatinine, globulin, glucose, LDH, AST, ALT, alkaline phosphatase, total bilirubin, total protein, albumin
- f. **LFTs:** ALT, AST, ALP, LDH, and bilirubin (total and direct)
- g. **Pregnancy Test:** For women of childbearing potential, regardless of birth control methodology
- h. **SF-36:** At visits where the SF-36 is evaluated the SF-36 must be the first assessment performed.
- i. **Follow-up visit:** to be completed approximately 2 weeks (+/- 7 days) after subject's last treatment or at the time of early treatment termination.

[figure not shown]

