### 3.5. Changes to the Protocol-Specified Analyses

For the method of assigning subject to treatment (as mentioned in Section 3.2), protocol states that the responders will initiate open-label fostamatinib treatment with the dose and regimen that was efficacious in achieving a stable platelet response in Study C-935788-047 or C-935788-048. In reality, the patients were not required to be stable responders but rather to have at least one platelet count of at least 50,000/ $\mu$ L.

The protocol defines the baseline value as the last measurement for the corresponding variable prior to the first randomized dose at Visit 3 in Study C-935788-047 or C-935788-048. For the analyses described by this SAP, the baseline value will be defined as the last measurement for the corresponding variable prior to the first dose of fostamatinib in Study C-935788-047 or C-935788-048 (for fostamatinib patients in the previous study) or the present study (for placebo patients in the previous study), unless specified otherwise in the SAP.

For secondary efficacy endpoint, duration of stable platelet response, has been changed to duration of platelet response, the protocol specified that subjects who drop out of the study before achieving a platelet response will be assigned duration of platelet response of 0 and will be censored. In addition to the duration of platelet response, total duration of platelet response is also defined in **Section 4.4** in this SAP and will be analyzed.

For secondary efficacy endpoint, subjects with reduction in the dose of concomitant ITP therapy while maintaining an adequate platelet count (yes/no), the protocol states that a two-sided, McNemar's test was to be performed to compare the proportions of subjects achieving a reduction in the dose of concomitant ITP therapy while maintaining an adequate platelet count between the fostamatinib and placebo treatments. In this SAP, no McNemar's test will be performed, instead the patient level of listing for the concomitant ITP therapy using during the present study will be provided in data listing.

Also, per protocol version 5, one-sample t-test was to be used to evaluate the mean change from baseline for each post-baseline time point for the safety endpoints of systolic and diastolic blood

pressure, liver function test [i.e., ALT, AST, alkaline phosphatase, and bilirubin (total, direct, and indirect)] and ANC. This one-sample t-test will not be performed.

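### SAP 11.4 takes the mean IBLS bleeding score over 24 months; protocol 10.5 takes it over the whole treatment period of up to 60 months, and SAP 3.5 does not list the change

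*SAP*

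**What the plan says.** The two documents define the across-visit IBLS mean over different periods.

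- Protocol 10.5: "The mean of the IBLS scores across visits during the treatment period will be summarized using descriptive statistics". No month limit is given.
- SAP 11.4, first IBLS bullet: "The mean of the IBLS scores across 9 anatomical sites and across visits during the 24-month treatment period in present study".

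The length of treatment is given elsewhere. Protocol 5.3 states: "Subjects will self-administer the study drug throughout the 60-month treatment period". Protocol 7.1.2 also allows up to 60 months. SAP 3.1 has subjects seen every month for the first year and a half and then gives this schedule: "followed by every-other-month visits for a maximum of 5 years of treatment or until commercial availability of drug, whichever comes first". SAP 3.2, however, calls the dosing period 24 months, and protocol 8.4 also still says 24 months.

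On collection, protocol 7.6.4 states: "Bleeding symptoms will be assessed using the IBLS at each study visit". SAP Table 1 schedules the bleeding assessment through Month 60, with the footnote "IBLS scale only; prior to Version 4, protocol used both IBLS and WHO bleeding scales". Of the WHO scale, protocol 7.6.4 says that it "was collected during the first 2 years of treatment" and was then dropped.

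SAP 3.5 records another departure from protocol 10.5, the tests of mean change from baseline: "This one-sample t-test will not be performed". It has no entry on the IBLS window.

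**The concern.** Long-term safety is the primary objective, and bleeding by IBLS is the first safety outcome named in protocol 10.5. The across-visit mean is the only IBLS summary that section specifies. A cut at Month 24 would remove the later part of follow-up from it without saying so.

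A two-year window has a stated basis for the WHO scale, whose collection stopped. It has none for the IBLS, which continued and became the only bleeding scale. The other safety summaries in the SAP carry no such limit: the laboratory shift tables (11.2) use the worst and last values in the present study, and the blood pressure counts (11.3) use any post-baseline time.

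The wording also leaves programming open. One programmer could filter at Month 24 and another could use all visits, and the two would produce different tables from the same plan.

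**Working it through.** There is no sample size or power figure to reproduce. The check compares the texts, counts the visits affected, and works out how far the two means can differ.

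**Inputs.** The visit schedule comes from protocol Table 2 and SAP Table 1: monthly through Month 18, then every second month to Month 60. I take the later visits as Months 20, 22, ..., 60. Day 1 and the post-treatment follow-up visit are excluded, and all scheduled visits are assumed attended.

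**Visit counts.** Through Month 24 there are 18 + 3 = 21 visits. Through Month 60 there are 18 + 21 = 39, so 39 − 21 = 18 fall after Month 24.

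**Difference in means.** Let w be the fraction of a subject's visits after Month 24, E the average score up to Month 24, and L the average after it.

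- SAP mean = E
- Protocol mean = (1 − w)E + wL
- Protocol mean − SAP mean = w(L − E)

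The difference is zero for a constant score and can go in either direction.

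| Treated to month | Visits | After Month 24 | w | Protocol − SAP |
|---|---|---|---|---|
| 24 | 21 | 0 | 0 | 0 |
| 30 | 24 | 3 | 0.125 | 0.13 (L − E) |
| 36 | 27 | 6 | 0.222 | 0.22 (L − E) |
| 48 | 33 | 12 | 0.364 | 0.36 (L − E) |
| 60 | 39 | 18 | 0.462 | 0.46 (L − E) |

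**Illustration (assumed pattern).** Each site is graded 0 to 2. One site of nine at grade 2 gives a visit average of 2/9 = 0.222. The nine-site average is used for both means.

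- No bleeding through Month 24, then grade 2 at one site at every later visit. The SAP mean is 0.00. The protocol mean is 0.222 × 6/27 = 0.049 at 36 months, 0.222 × 12/33 = 0.081 at 48, and 0.222 × 18/39 = 0.103 at 60.
- The reverse pattern. The SAP mean is 0.222. The protocol mean is 0.222 × 21/27 = 0.173 at 36 months and 0.222 × 21/39 = 0.120 at 60.

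So the SAP version can understate or overstate the whole-period mean.

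**The case against.** The strongest reply is that the phrase is a stale label and not a data cut. SAP 11.4 does not say through Month 24. SAP 3.2 uses the same words for the entire dosing period, and protocol 8.4 carries a similar leftover. On that reading the SAP means the whole treatment period and misstates its length, and SAP 3.5 would have nothing to list.

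This is plausible, and the documents do not settle the intent. But the phrase in 11.4 sits inside an analysis rule, where it determines which visits enter the calculation. The figure in protocol 8.4 does not. Whichever reading is right, the wording has to be resolved.

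The second reply is that little is lost even on the literal reading. This largely stands. The next bullet of SAP 11.4 summarises the highest and total IBLS by visit without a limit, and adverse events cover the whole study (SAP 11.1). No test or decision rule uses the across-visit mean. The by-visit tables do not reproduce it, however: they describe whoever remains at each visit, while the mean pools each subject's own visits.

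The third reply is that the size is hypothetical: 60 months is a ceiling that commercial availability can shorten, and the number treated beyond Month 24 is unknown. That also stands.

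A possible objection to dividing by nine, because the form in protocol Appendix 7 has eleven rows, fails. Skin and oral bleeding each appear twice there, by examination and by history, and protocol 7.6.4 states nine sites.

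**Conclusion.** The concern holds. As written, SAP 11.4 narrows a protocol-specified safety summary from up to 60 months to 24, contrary to the SAP's own design section and visit schedule, and does not list the change. Whether the restriction was intended is unknown.

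The affected share of scheduled visits runs from none for subjects who stop by Month 24 to 46% at the 60-month ceiling. The effect on a subject's mean is that share times the late-minus-early difference in score; in the illustration above it is about 0.05 at 36 months and 0.10 at 60 months, on a 0 to 2 scale. These figures assume full attendance at scheduled visits. Actual treatment durations and score changes are not in the documents, so the effect on the reported summary could be negligible. It reaches one descriptive table and no test or efficacy result. It should be corrected because the correction is simple and the table bears on the primary objective.

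**What to change.** 1. In the first IBLS bullet of SAP 11.4, replace the 24-month wording with: *at all treatment-period visits (up to Month 60)*.
2. Keep the 24-month window in SAP 11.4 for the WHO scale only.
3. Correct the 24-month dosing period in SAP 3.2 to agree with SAP 3.1.
4. If a 24-month IBLS window is intended, list it with its reason in SAP 3.5 and present the whole-period mean beside it.

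The 24 months in protocol 8.4 is editorial and can wait for the next amendment. The cost is two phrases in the SAP, with no protocol amendment, new assessments or new data.
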